4.1. Trial design

RATE-AF is a Prospective, Randomised Open-label Blinded Endpoint (PROBE) clinical trial comparing the use of Digoxin and beta-blockers (Bisoprolol) as initial rate control therapy. This study also designed to assess the feasibility of conducting a future clinical event trial. See Appendix B for trial schema.

4.2. Trial interventions

Digoxin 62.5-250 µg od
Bisoprolol 1.25-15 mg od

4.3. Primary outcome measure

The primary outcome is the Patient-reported Quality of life (QoL) SF-36v2 Physical Component Summary (PCS) score at 6 months.

4.4. Secondary outcome measures

Patient-reported QoL:

- SF-36 global and domain-specific scores at 6 and 12 months
- EQ-5D-5L summary index and visual analogue scale at 6 and 12 months
- AFEQT overall score at 6 and 12 months

Cardiac function:

- Echocardiographic LVEF at 12 months
- Diastolic function (E/e' and composite of diastolic indices) at 12 months
- Change in heart rate using 24-hour ambulatory ECG

Functional assessment:

- Six-minute walking distance at 6 and 12 months
- Change in European Heart Rhythm Association (EHRA) class at 6 and 12 months

Biomarkers:

- Change in B-type natriuretic peptide (BNP) levels at 6 and 12 months

Feasibility outcomes:

- Recruitment target of 3 patients per week across all participating centres
- Compliance and reasons for non-compliance
- Number of withdrawals and losses to follow-up (with reasons)
- Drug discontinuation rate and adverse reactions requiring drug discontinuation

- Number of patients needing therapy-induced requirement for additional treatment
- Cardiovascular events (mortality, thromboembolic events, myocardial infarction and cardiovascular intervention)
- Population-specific standard deviations (SD) and proportions for all outcomes

4.5. Timing of outcome assessments

The schedule of trial procedures and outcome assessments are given in Appendix C.

4.6. Randomisation

Participants will be randomised in a 1:1 ratio to either Digoxin 62.5 – 250 µg od or Bisoprolol 1.25 – 15 mg od. The time between randomisation and commencement of trial therapy should be minimised (ideally <24 hours).

Randomisation will be provided by a computer generated programme at the Birmingham Clinical Trials Unit (BCTU), using a minimisation algorithm incorporating the following factors:

- Baseline EHRA (class 1/2a and class 2b/3/4)
- Gender (Male and Female)

4.7. Sample size

Randomising 144 patients we can assume an 85% power to detect an effect size of half a standard deviation in a continuous outcome measure of QoL (two-sided alpha of 0.05).

A sample size of 160 patients would account for an estimated 10% loss to follow-up (including withdrawal and death prior to 12-month assessment).

There is some evidence from existing research to support the notion that the treatment effect could be this large. The mean SF-36 role-physical score from the rate-control arm of the RACE study was 47, with a 17% improvement with rate-control over time.² In another study, CCB resulted in 22% improvement in a proprietary symptom-checklist, compared to a non-significant 8% change in those assigned to beta-blockers (SD 10-points in both groups). These values are also consistent with a 17% improvement in SF-36 scores in a third trial, PIAF.³

4.8. Framework

The objective of the trial is to test the superiority of one intervention to another as well as to assess the feasibility of running a future clinical event study.

Null Hypothesis for primary outcome:

No difference in the SF-36v2 PCS score when comparing a strategy of digoxin versus beta-blocker therapy for initial rate control in patients with permanent AF.

Alternative Hypothesis:

Use of digoxin or beta-blocker therapy as initial rate control in patients with permanent AF is superior based on the PCS score from SF-36v2.

4.9. Interim analyses and stopping guidance

A joint oversight committee comprising a Trial Steering Committee (TSC) and Data Monitoring Committee (DMC) will be engaged for this trial. The role of the TSC is to provide the overall supervision of the trial. The TSC will

monitor trial progress and conduct and advice on scientific credibility. The TSC will consider and act, as appropriate, upon the recommendations of the Data Monitoring Committee. Further details of the remit and role of the TSC are available in the TSC Charter.

An independent DMC will be established to oversee the safety of participants in the trial. The DMC will meet prior to the trial opening to enrolment, and then meet at least annually, or as per a timetable agreed by the DMC prior to trial commencement. Data analyses will be supplied in confidence to the DMC, which will be asked to give advice on whether the accumulated data from the trial, together with the results from other relevant research, justifies the continuing recruitment of further participants. The DMC will operate in accordance with the trial specific charter. It is likely that the Haybittle-Peto boundary will be used. This states that if an interim analysis shows a probability of less than 0.001 that the treatments are different, then the trial should be stopped early. This will be used alongside data on important secondary endpoints and all other relevant evidence. A DMC report and charter outlining the terms of reference (including information on stopping rules) will be agreed with the DMEC.

4.10. Pilot Progression Rules

N/A

4.11. Timing of final analysis

The final analysis for the trial will occur after last randomised participant completes their 12-month follow-up and the corresponding outcome data has been entered onto the trial database and validated as being ready for analysis. This is provided that the trial has not been stopped early for any reason (e.g. DMC advice or funding body request).

4.12. Timing of other analyses

N/A

4.13. Trial comparisons

All references in this document to 'group' refer to Digoxin or Bisoprolol.

5. Statistical Principles

5.1. Confidence intervals and p-values

All estimates of differences between groups will be presented with two-sided 95% confidence intervals, unless otherwise stated. P-values will be reported from two-sided tests.

5.2. Adjustments for multiplicity

No correction for multiple testing will be made.

5.3. Analysis populations

All primary analyses (primary and secondary outcomes including safety outcomes) will be by intention-to-treat (ITT). Participants will be analysed in the intervention group to which they were randomised, and all participants shall be included whether or not they received the allocated intervention.

As a sensitivity analysis, a per-protocol analysis may also be carried out for the primary outcome if it is deemed a worthwhile investigation to further understand drug efficacy. See section 5.4 for how adherence information will be summarised. See section 9.10 for further details on any sensitivity analyses.

5.4. Definition of adherence

Data on adherence to medication was collected at each follow up visit and captured in two ways:

1. By asking the patients if they have taken "All", "Some" or "None" of their medication
 - i) If patients have taken "Some" of their medication, then further asked if they have taken ">75%", ">50-75%", ">25-50%" or "≤25%"
2. By assessing the data on any oral medications that patient is taking to normalise their heart rate

Hence treatment adherence will be summarised in both ways described above and will be summarised separately for 6 and 12 months.

Per-Protocol population set:

Since the primary outcome for this study is at 6-months, the per-protocol population will therefore form of only those patients that have remained adherent to their treatment allocation at 6 months. Adherence to treatment allocation will be based on data collected on oral medication that the patients are taking at 6 months. Hence adherence will be computed as a binary "yes/no". The per-protocol set will therefore consist of patients that remained adherent to their treatment allocation at 6 months (based on data from oral medications) as well as those patients that remain in atrial fibrillation, as documented on the AFEQT questionnaire at 6 months.

Patients could also be taking additional rate control therapy beyond their randomised treatment allocation and so although not part of definition for adherence, this data will also be summarised by treatment arm. Similarly we also collect data on compliance by asking patients at each visit if they have been compliant with drugs used to control heart rate and so this data will also be summarised by treatment arm.

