4.1 Inclusion Criteria

- Adult patients aged 60 years or older
- Permanent AF, characterised (at time of randomisation) as a physician decision for rate-control with no plans for cardioversion, anti-arrhythmic medication, or ablation therapy
- Symptoms of breathlessness (New York Heart Association Class II or more)
- Able to provide written informed consent

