8.2 Up-Titration Visits

For the majority of participants, two up-titration visits will be planned to supervise the appropriate use of medications as per the up-titration schedule (see **Appendices A and B**). Additional up-titration visits, as required, are acceptable in order to attain a heart rate at rest of ≤ 100 bpm.

Up-titration visits will involve the following procedures:

- Record adverse events as reported by the participant or observed by the investigator.
- Review of medications and plan for trial drug up-titration
- Assessment of compliance
- Symptom-directed clinical examination
- Vital signs, including heart rate and blood pressure
- Administer QoL and functional capacity questionnaires (last up-titration visit only).
- Organise a 24-hour ambulatory ECG once up-titration completed (results to be forwarded to the clinician).

8.3 Visit 2, Month 6

Visit 2 will occur at an interval of six months (\pm four weeks) after the Baseline Visit and involve the following procedures:

- Administer QoL and functional capacity questionnaires.
- Record adverse events as reported by the participant or observed by the investigator.
- Confirm current rate control therapy (including dosage) and check concomitant medications.
- Assessment of compliance.
- Collect blood samples for biomarker analysis.
- Collect blood sample for serum digoxin concentration, potassium and creatinine as part of standard clinical care.
- Record time in therapeutic range for patients on anticoagulation with vitamin-K antagonists and compliance in patients receiving non-VKA oral anticoagulants.
- Obtain a twelve lead ECG.
- Record the results of physical examinations and vital signs.
- Supervise a 6-minute walk test, recording distance walked and peak heart rate.
- Complete other CRF requirements.
- If an echocardiogram has been performed for clinical reasons since the previous visit, images will be retrieved and sent to the core echocardiographic laboratory.

- Confirm appointment date for Visit 3.

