9.5.2 Data Collection for PROMs

PROMs will be assessed at all main visits (Baseline, 2 and 3) and at the participants final up-titration visit (if applicable). The QoL tools used will be EQ-5D-5L, SF-36 and AFEQT. To avoid introducing co-intervention bias, all QoL data will be kept confidential and will not be used to inform clinical care.⁸⁴ Patients will be advised of this in the patient information sheet. PROMs will be collected at the start of each visit, before other trial procedures. In cases where the visit coincides with a clinician review, questionnaires should be completed in advance. The feasibility of using an online data collection tool will be explored, administered by trained research nurses and according to good-practice guidelines.⁸⁵ We will use this trial to perform an initial small-group assessment of electronic PROMs-equivalence to inform a future clinical event trial.

Qualitative research will be performed using a focus group of 10 volunteer patients enrolled at the start of the trial (5 in each randomised group). The focus group will meet after up-titration and then at 6 and 12 months. Detailed methods will be established before the first meeting, in collaboration with the University of Birmingham Qualitative Research Group.

All staff will receive training in QoL collection, with specific guidance on reducing introduced bias, minimising missing data and coaching participants to use the QoL software. Levels of missing PROMs data will be monitored. The site personnel responsible for collection of patient reported outcomes will be the Research Nurse under the supervision of the Principal Investigator.

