Secondary objectives are as follows:

- Generic and AF-specific patient-reported QoL using the SF-36 global and domain-specific scores, the AFEQT overall score and the EQ-5D-5L summary index and visual analogue scale at 6 and 12 months.
- Echocardiographic left-ventricular ejection fraction (LVEF) and diastolic function (E/e' and composite of diastolic indices) at 12 months.
- Functional assessment, including 6-minute walking distance achieved, change in European Heart Rhythm Association (EHRA) class and cognitive function at 6 and 12 months.
- Change in B-type natriuretic peptide (BNP) levels as a surrogate for total cardiac strain at 6 months.
- Change in heart rate from baseline and group comparison using 24-hour ambulatory ECG.

Feasibility objectives:

- Successful methods for recruitment
- Key issues that affect retention of participants, such as convenience, compliance and cross-over (target

of 85% study completion rate).

- Drug discontinuation rate and adverse reactions leading to drug discontinuation.
- Therapy-induced requirement for additional treatment (e.g. pacemaker implantation).
- Population-specific standard deviations and proportions to enable sample size calculation for a future trial.
- Assessment of cardiovascular outcomes including a composite of adverse clinical events (mortality, thromboembolic events, myocardial infarction and cardiovascular interventions).

4. Trial methods

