The data for the composite of diastolic indices is a binary (yes/no) and will be computed as described in the data manipulations section 9.4. This data is collected at baseline and 12 months and will be summarised as number and percentage by treatment arm and time-point. The analysis for this outcome will be conducted using a logistic regression model, where the outcome will be the binary category (yes/no) at 12 months and independent variables in the model being the baseline category, treatment arm, all minimisation variables, age at randomisation and baseline LVEF. An adjusted odds ratio and 95% confidence interval will be estimated from the logistic regression model.

- **Change in heart rate**

The data type for heart rate is continuous in nature. This data is collected at baseline, 6 months and at 12 months. The mean and standard deviation along with minimum and maximum values will be presented by treatment arm and time-point for 1) Radial heart rate, 2) Apical heart rate, 3) 12-lead ECG heart rate, and 4) 24-hour ambulatory average heart rate. The 24-hour ambulatory heart rate is only measured once and so no baseline score will be there to adjust for it in analysis.

These outcomes will be analysed using the same analysis methods as described in section 9.5 for primary outcome and analysis will be done separately for 6 and 12 month time-points.

A scatter plot of radial vs apical heart rate at each time point will be produced to visualise the radial-apical discrepancy.

Functional assessment

- **Six-minute walking distance at 6 and 12 months**

The data for this outcome is continuous in nature and this test is conducted at baseline, 6 months and 12 months. The time (measured in min/s) and distance (measured in metres) are only recorded if the patient did the test. Therefore this data will be summarised by treatment arm and time-point with respect to the number of patients conducting the test, the mean and standard deviation, median and IQR as well as minimum and maximum values for time and distance covered. Reasons for stopping the test prematurely were also collected and so this will also be summarised by treatment arm and time-point.

The main endpoint for this outcome is the distance (in metres) walked and so this will be analysed using the same analysis methods as described in section 9.5 for primary outcome and analysis will be done separately for 6 and 12 month time-point.

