Appendix D5: Primary outcome results

SF-36v2 physical component summary (PCS) score at 6 months

Primary outcome	Time point	Statistic	Digoxin	Bisoprolol	Linear regression model	
					Adjusted mean difference ¹ 95% CI	P-value ¹
Intention to treat analysis						
PCS	Baseline	N Mean [SD] Min - Max			-	-
	6 months	N Mean [SD] Min - Max				
Sensitivity Analysis – Multiple imputation for missing data						
PCS	Baseline	N Mean [SE]			-	-
	6 months	N Mean [SE]				
Per-Protocol analysis (i.e. adherent to treatment allocation and remained in permanent AF at 6 months)						
Included in per-protocol analysis set	6 months	No			-	-
		Yes				
		Total				
PCS	Baseline	N Mean [SD] Min - Max			-	-
	6 months	N Mean [SD] Min - Max				

¹-Adjusted for treatment arm, baseline score, all minimisation variables, age at randomisation and baseline LVEF

Reference group for the treatment arm in the model is Bisoprolol arm

Higher values indicate better scores so a positive mean difference favours Digoxin arm

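### SAP 5.4 takes rhythm at 6 months from the patient's AFEQT answer although a 12-lead ECG is scheduled at that visit, so the per-protocol sensitivity analysis may exclude or keep the wrong patients

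*SAP*

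**What the plan says.** SAP 5.4 builds the per-protocol set from two elements. One is adherence at 6 months, judged from the recorded oral medications. The other is rhythm: "as well as those patients that remain in atrial fibrillation, as documented on the AFEQT questionnaire at 6 months". The SAP's objectives place the AFEQT among the patient-reported instruments ("Generic and AF-specific patient-reported QoL using the SF-36 global and domain-specific scores, the AFEQT overall score"), and SAP 5.6 confirms that patients know their treatment. Protocol 9.5.2 fixes the order within a visit: "PROMs will be collected at the start of each visit, before other trial procedures". The AFEQT answer therefore comes before that visit's ECG.

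Protocol 8.3 lists "Obtain a twelve lead ECG" among the Month 6 procedures. Both schedules of assessments (Protocol Table 1, SAP Appendix C) agree, and Protocol 9.1 treats the ECG as standard care at every trial visit. The only variable the SAP takes from this ECG is rate ("3) 12-lead ECG heart rate", SAP 9.6).

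Appendix D5 labels the analysis set "adherent to treatment allocation and remained in permanent AF at 6 months" and does not say where AF status comes from. On the standing of the analysis, SAP 5.3 says "a per-protocol analysis may also be carried out for the primary outcome if it is deemed a worthwhile investigation", whereas SAP 9.10 lists it among the sensitivity analyses that will be done.

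**The concern.** Rhythm can be observed directly. Here it is taken from an unblinded patient's answer on a quality-of-life form, when a direct observation is scheduled for the same day. Two consequences are possible.

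The first is plain misclassification: patients still in AF are dropped, or patients out of AF are kept.

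The second matters more. The primary outcome is the same patient's self-reported physical score at the same visit. If patients who feel better are more inclined to say they are no longer in AF, the set is selected after randomisation on something close to the outcome. Because treatment is open-label, that selection could differ between arms. SAP 5.3 intends the analysis to clarify drug efficacy, and a selection rule linked to the outcome works against that aim. A reader of Appendix D5 would also not learn that AF status was self-reported.

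**Working it through.** **1. The plan's own figure.** SAP 4.7 gives 144 evaluable patients for a difference of 0.5 SD, 85% power and two-sided alpha 0.05. The normal approximation gives 2 × (1.960 + 1.036)² / 0.5² = 71.8, so 72 per arm and 144 in all, with power 0.851 (0.846 by the t-test). Allowing for 10% loss, 144 / 0.9 = 160. The design reproduces, and nothing below changes it.

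**2. What the documents give on misclassification.** They do not give the wording of the AFEQT item, its accuracy, the expected share of patients leaving AF, a check of the answer against the ECG, or a rule for a missing or discordant answer. No count can be derived from them.

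**3. Scale, with every input assumed.** Take N = 144 before any adherence exclusions and treat the ECG as error-free. Let p be the share truly in AF at 6 months, *se* the chance that a patient in AF reports AF, and *sp* the chance that a patient out of AF reports no AF.

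- Wrongly excluded = 144 × p × (1 − *se*)
- Wrongly kept = 144 × (1 − p) × (1 − *sp*)

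| p | *se* | *sp* | Wrongly excluded | Wrongly kept |
|---|---|---|---|---|
| 0.90 | 0.99 | 0.50 | 1.3 | 7.2 |
| 0.90 | 0.95 | 0.80 | 6.5 | 2.9 |
| 0.98 | 0.95 | 0.80 | 7.1 | 0.6 |
| 0.98 | 0.90 | 0.80 | 14.1 | 0.6 |
| 1.00 | 0.80 | any | 28.8 | 0.0 |

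Over p from 0.90 to 1.00, *se* from 0.80 to 0.99 and *sp* from 0.50 to 0.80, about 1 to 29 patients are wrongly excluded and 0 to about 7 wrongly kept.

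**4. Wrong against right exclusions.** If 2% are out of AF, 144 × 0.02 = 2.9 patients could correctly be excluded. With reporting errors of 2%, 5% and 10% among those in AF, 141.1 × 0.02, 0.05 and 0.10 gives 2.8, 7.1 and 14.1 wrongly excluded. If instead 10% are out of AF (14.4 patients), a 5% error wrongly excludes 129.6 × 0.05 = 6.5, against 14.4 × 0.80 = 11.5 correctly excluded at *sp* = 0.80. Whether wrong exclusions outnumber right ones therefore depends on the assumed rate of leaving AF.

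**5. Precision.** Over the same ranges, power for 0.5 SD in the per-protocol set is 0.73 to 0.85 under the AFEQT rule and 0.81 to 0.85 under the ECG rule. The ECG rule does not always give more power. At p = 0.90, *se* = 0.99 and *sp* = 0.50, the AFEQT rule retains 135.5 patients (power 0.829) and the ECG rule 129.6 (0.812), because the AFEQT rule keeps patients who are out of AF. The case for the ECG is that it selects the intended patients without reference to how they feel.

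**6. Reach.** SAP 5.3 makes all primary analyses intention-to-treat, and AF status at 6 months plays no part in them. The criterion touches one sensitivity analysis of one outcome.

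**The case against.** The strongest reply has four parts.

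- **No documented error or mechanism.** Nothing in the documents shows that the AFEQT answer is inaccurate or that it tracks the physical component score. This stands. It limits the point to a risk and rules out stating a direction of bias.
- **The ECG is not the entry definition.** Protocol 4.1 has "Permanent AF, characterised (at time of randomisation) as a physician decision for rate-control", with no ECG criterion, and one tracing shows rhythm at one moment only. This is true, but it does not favour a questionnaire. SAP 5.4 asks whether the patient remains in AF at 6 months, and an ECG answers that for the visit more directly than the patient's recollection.
- **Narrow scope.** The analysis is optional under SAP 5.3, and no decision rule depends on it. This stands, and it caps the importance of the point. However, SAP 9.10 lists the analysis as planned, and Appendix D5 sets its rows beside the primary result.
- **Cost.** The SAP names only heart rate from the 12-lead ECG, so rhythm may not be a CRF field. This stands, and the fix is conditional on it.

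A reader might go further and infer that patients will certainly be misclassified, or that the trial's main result is compromised. The documents support neither: they give no error rate, and the main result does not use this set.

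**Conclusion.** The point holds as a cheap improvement to one sensitivity analysis. The text establishes that per-protocol AF status rests on a self-report by unblinded patients, that a 12-lead ECG is scheduled at the same visit, and that no rule connects the two. That self-report may misclassify rhythm, and that the error may be related to the self-reported primary outcome, is a reasonable inference but is not documented.

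The number affected is unknown. The range of about 1 to 29 wrongly excluded and 0 to about 7 wrongly kept, of 144, rests wholly on the assumed values in the working. The documents support no direction or size of bias in the treatment effect. The intention-to-treat analysis and the 144/160 sample size are unaffected.

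**What to change.** In SAP 5.4:

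- Define AF status at 6 months by the rhythm on the Visit 2 12-lead ECG, where rhythm is recorded or can be read from the existing tracing.
- Use the AFEQT answer only when that ECG is missing. This fallback is needed because Protocol 8.7 mails questionnaires to patients who stop trial treatment but agree to follow-up, and they may have no visit ECG.
- State that adherence and remaining in AF are both required. The present linking phrase can be read as adding a second group of patients, whereas Appendix D5 implies both conditions.
- Cross-tabulate ECG rhythm against the AFEQT answer by arm, so that disagreement is visible.

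In Appendix D5, name the source of AF status. While editing, align SAP 5.3 (optional) with SAP 9.10 (planned).

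The cost is SAP wording if rhythm is already a CRF field. If it is not, the Month 6 tracings must be retrieved, read and entered, at most one for each of the 160 participants. No new visit or procedure is needed.
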